[figure not shown]

**A Research on the Ovarian Function Detection and Protection in
Fertility Preservation Surgery for Ovarian Malignancy**

2019.02.01

Study objectives The primary objective of this study is to identify whether applying GnRHa on patients with ovarian malignancy for fertility preservation surgery preoperatively and postoperatively has a different outcome. By comparing the physical and hormone indexes in the control group and experimental group, we plan to find out the effect of GnRHa.

Trial design This is a prospective interventional trial. After signing of informed consent, the electronic medical data of patients with ovarian malignancy will be collected in this study. 20 patients will be enrolled in this trial. They will be randomized into the control group and the experimental group as to receive GnRHa for fertility preservation surgery preoperatively and postoperatively. We plan to investigate into the effect of GnRHa by monitoring the physical ovarian change and the six hormone indexes in the two different groups.

Sample size The planned sample size was based on data from a previous study, in which the standard deviation was 5. We assumed an one-tailed α error of 0.05 and a sampling error of 1.0. We propose to enroll 24 participants including 12 patients in the control group and the others in the experimental group, and allow for a dropout rate of 10% for an effective sample size of 20.

Inclusion criteria

1. Volunteer to participate in the study with informed consent;
2. Females aged 10-90 who are confirmed with ovarian malignancy and are willing to receive fertility preservation surgery.

Exclusion criteria

1. Suspected or identified as other tumors of genital tract;
2. History of hyperparathyroidism, infectious diseases (tuberculosis, AIDS), autoimmune diseases, or digestive system diseases (malabsorption, crohn disease and dysentery);
3. Other diseases or heavy injuries that will interfere with the results;
4. Simultaneous participation in another clinical study with investigational medicinal product(s) or researcher thinks the subjects are not suitable for this trial.

Withdrawal Subjects must be withdrawn from the study when one of the following criteria occurs:

1. At their own request. At any time during the study and without giving reasons, a subject may decline to participate further. The subject will not suffer any disadvantages as a result;

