2. In the investigator's opinion, continuation of the study treatment would be harmful to the subject's health;
3. Obvious non-compliance;
4. Lost to follow-up;
5. Pregnancy;
6. Other medical or surgical treatments of endometrial carcinoma.

Safety assessments

Safety will be assessed by renal and liver function test, electrolyte, routine blood test. Other indicators are detected during the operation and rehabilitation period. The occurrence of any adverse events in participants will be recorded in the case report forms during each patient visit. We will withdraw patients who have severe adverse events, as it is unsafe for them to continue the trial. Meanwhile, we will give them relevant medical care and follow them up until the reaction has terminated.

Statistic analysis

Before the enrollment of participants, patients' medical data will be collected and analyzed to evaluate whether they are suitable for this trial. With their informed consent, they will be randomized into the control group and the experimental group. The situation of the two group will be almost the same considering the average age, the average BMI, the average grading evaluation. The fertility preservation surgery means the ovary affected by cancerous cell is resected when the other is preserved. If the other side was already resected, the ovarian tumor on the affected side will be removed. Before and after the operation, patients in the control group will receive placebos when the experimental group will receive GnRH_a. The physical ovarian volume, six hormone indexes, AMH and the ovulating period will be monitored and compared by chi-square analysis in SPSS 17.0.

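### Chi-square is the only between-group test named, yet at least eight of the nine listed outcomes are continuous and no cut-off is defined

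*Combined protocol and SAP*

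**What the plan says.** The combined protocol and SAP describes its between-group testing in the last sentence of the Statistic analysis section: "The physical ovarian volume, six hormone indexes, AMH and the ovulating period will be monitored and compared by chi-square analysis in SPSS 17.0". It names no t test, rank test, analysis of covariance or other method for measured values, and it gives no threshold, category or responder definition for any outcome.

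The Study objectives section makes this comparison the route to the primary objective: "By comparing the physical and hormone indexes in the control group and experimental group, we plan to find out the effect of GnRHa".

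The Sample size section rests on a previous study "in which the standard deviation was 5", without naming the outcome or its unit. It continues: "We assumed an one-tailed α error of 0.05 and a sampling error of 1.0". It plans 24 participants, 12 of them controls, and would "allow for a dropout rate of 10% for an effective sample size of 20".

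**The concern.** The test does not fit the data. Chi-square asks whether counts fall into categories in the same proportions in both arms. A volume or a hormone concentration has no categories until someone creates them. The plan's own sample size uses a standard deviation, which a comparison of proportions would not need, so the planners appear to have had a continuous measure in mind.

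Three things are at stake. The main comparison has no defined form, so an analyst must make an unplanned choice for each of at least eight outcomes. Cutting a continuous measure in two usually discards power, and a trial of 20 to 24 patients has little to spare. Nothing prevents the cut-offs from being chosen after the results are known, which would inflate the false-positive rate.

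**Working it through.** **Inputs from the document.** Test: chi-square only (Statistic analysis). Outcomes: volume 1 + hormones 6 + AMH 1 + ovulating period 1 = 9. The first three items are continuous, 1 + 6 + 1 = 8. The type of the ninth is not defined, hence at least eight. Level: 0.05, one-tailed (Sample size). Arm sizes: 12 as enrolled, 20/2 = 10 at the effective size.

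**The plan's own figure.** The plan states no power or effect size for this comparison, so there is none to reproduce. The dropout step is acceptable: 20/0.9 = 22.2, so 23, or 24 for equal arms. The effective size of 20 does not follow from the stated inputs; for example (1.645 × 5/1.0)² = 67.6, so 68 for one mean. That is a separate problem, and this point does not depend on it.

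**Chi-square on ungrouped values.** Suppose 20 patients, 10 per arm, all with different values. The table is 2 × 20 with one patient per column, so every expected count is 0.5. Each of the 40 cells contributes (0.5)²/0.5 = 0.5, whether it holds 1 or 0. The total is 40 × 0.5 = 20 on (2 − 1)(20 − 1) = 19 degrees of freedom, p = 0.39. The result is the same for every possible treatment effect.

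**Chi-square after a median split.** With n per arm and no effect, the number a above the median in one arm has probability C(n,a)²/C(2n,n). For n = 10, one-tailed:
- Yates or Fisher rejects at a ≥ 8: (2025 + 100 + 1)/184,756 = 1.15%.
- Uncorrected Pearson also rejects at a = 7: (14,400 + 2,126)/184,756 = 8.94%.

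Power below assumes a 1 SD effect, normal data and equal arms. None of these is in the plan. The t test uses the noncentral t with 2n − 2 degrees of freedom and noncentrality d√(n/2), where d is the effect in SDs; the split was simulated. The actual error rate of the split is in brackets.

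| Per arm | Level | Median split, chi-square | t test |
|---|---|---|---|
| 10 | one-tailed 5% | 30% Yates or Fisher (1.2%); 67% uncorrected (8.9%) | 69% |
| 11 | one-tailed 5% | 56% (4.3%) | 73% |
| 12 | one-tailed 5% | 45% (2.0%) | 77% |
| 10 | two-sided 5% | 30% (2.3%) | 56% |
| 11 | two-sided 5% | 22% Yates (0.9%); 56% uncorrected (8.6%) | 61% |
| 12 | two-sided 5% | 45% (3.9%) | 65% |

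The Wilcoxon test keeps most of the t test's power: two-sided, 51% with 10 per arm and 60% with 12.

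**Other cut-offs.** A fixed cut-off at the control arm's 25th, 50th, 75th or 90th percentile, uncorrected and two-sided, gives 15%, 33%, 38% and 27% with 10 per arm, and 22%, 45%, 52% and 36% with 12. The Yates correction lowers all of these.

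**Cut-off chosen after the fact.** Under no effect, take the smallest two-sided p over all cut-points that leave at least 5 patients on each side. The false-positive rate is about 17% uncorrected or 9% with Yates (10 per arm), and 26% or 13% (12 per arm).

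**The case against.** The strongest reply is that chi-square is loose wording, and that whoever runs the analysis would use a t test. That may be so, but the document does not say it, and if true the correction costs almost nothing.

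A second objection concerns size. The 1 SD effect is assumed. The only ratio the plan offers is 1.0/5 = 0.2 SD, and only if its undefined sampling error means a difference between arms. At 0.2 SD with 10 per arm, two-sided power is 3% for the split and 7% for the t test, so changing the test would not rescue the trial. This stands: the mismatch of test and data is the main ground, and the power figures only illustrate its cost.

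Third, the loss varies. With 10 per arm, one-tailed and uncorrected, the split reaches 67% against 69%, but it does so at an 8.9% error rate. More favourable cut-offs narrow the gap without closing it: at the control arm's 75th percentile, one-tailed and uncorrected, power is 57% against 69% with 10 per arm and 64% against 77% with 12.

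Finally, the test can literally be computed on ungrouped data. It is the meaning that is lost, and the point is worded accordingly. The six hormones are not named, but treating hormone levels as measured concentrations is reasonable.

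**Conclusion.** The concern holds and must be fixed. The only test named does not suit at least eight of the nine outcomes, and those outcomes carry the primary objective. This conclusion rests on the text alone and needs none of the simulated figures.

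The size of the loss does depend on assumptions. At the plan's one-tailed level and 1 SD, the median split falls short of the t test by 77 − 45 = 32 percentage points with 12 per arm. With 10 per arm the shortfall is 69 − 30 = 39 points with a corrected test; it nearly vanishes uncorrected, but only because the error rate then exceeds 5%. The false-positive rates of up to about 26% are a worst case that requires searching for the cut-off.

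**What to change.** In the Statistic analysis section, replace chi-square for ovarian volume, the six hormones and AMH with one named test for continuous data: a two-sample t test (on the log scale for outcomes expected to be skewed) or the Wilcoxon rank-sum test. Fix the choice for each outcome, including the scale, before any data are seen. State the level and sidedness, and report the between-arm difference with a confidence interval. Where a pre-treatment hormone or AMH value is already collected, use analysis of covariance adjusting for it.

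Define the ovulating period. Keep chi-square or Fisher's exact test only for an outcome with predefined categories, for example the ovulating period if it is scored yes or no; with about 10 per arm, small expected counts would favour Fisher. The same text should name the assessment time for each comparison, since the Statistic analysis section gives none and a free choice of time point would reopen the problem.

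The cost is a few lines of wording, plus one degree of freedom per analysis where a baseline value is used, with no extra patients. The change does not deal with multiplicity across nine outcomes or with the small sample size.

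### Nine outcomes go to chi-square with no primary outcome, multiplicity rule, efficacy time point or cut-points, so any one nominally significant result could be reported as the effect of GnRHa

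*Combined protocol and SAP*

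**What the plan says.** The Study objectives section asks whether giving GnRHa for "fertility preservation surgery preoperatively and postoperatively has a different outcome", and continues: "By comparing the physical and hormone indexes in the control group and experimental group, we plan to find out the effect of GnRHa". This is an aim stated over a group of measurements, with none singled out.

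The Trial design section describes "monitoring the physical ovarian change and the six hormone indexes in the two different groups", which is seven quantities. The Statistic analysis section gives the longest list and the only method: "The physical ovarian volume, six hormone indexes, AMH and the ovulating period will be monitored and compared by chi-square analysis". It states no cut-points, significance level, testing order or success rule.

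The only alpha is in the Sample size section: "We assumed an one-tailed α error of 0.05 and a sampling error of 1.0". The standard deviation of 5 and the sampling error of 1.0 are tied to no named outcome, so the sample size does not reveal a primary outcome either.

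Two sentences mention timing, and neither fixes an efficacy assessment. "Other indicators are detected during the operation and rehabilitation period" is in the Safety assessments section and names no efficacy outcome. "Before and after the operation, patients in the control group will receive placebos when the experimental group will receive" GnRHa, in the Statistic analysis section, says when treatment is given, not when outcomes are measured.

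**The concern.** The trial is randomised and placebo-controlled, and it states a primary objective, so its result will be read as an answer about GnRHa. With nine comparisons and no rule for which one counts, the answer can be picked after the data are seen: the outcome, the measurement time, and the point at which a continuous value is cut to make a table. A chance finding on one of them would meet the stated aim as well as a real effect would.

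The choice of test adds a second problem. Ovarian volume, hormone levels and AMH are measured on continuous scales. Chi-square requires them to be grouped, which discards information in a trial with an effective size of 20.

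**Working it through.** **Inputs from the plan.**
- Outcomes: 1 (volume) + 6 (hormones) + 1 (AMH) + 1 (ovulating period) = 9.
- Effective size 20, hence 10 per arm. The plan's dropout step reproduces per arm: 10/(1 − 0.10) = 11.1, rounded up to 12, or 24 enrolled.
- The plan states no error rate for the nine comparisons, so there is no figure of its own to reproduce.

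**Assumptions.** Each outcome is tested at 0.05, there is no true effect, and outcomes are independent unless a correlation is given. All nine are cut in the same way.

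**1. Median split, two-sided.** Ten of 20 patients are high. If *a* of them are in one arm, chi-square = 20(20*a* − 100)²/10⁴.
- *a* = 7: 3.2, p = 0.074, not significant.
- *a* = 8: 7.2, p = 0.007, significant. With continuity correction it is 5.0, p = 0.025, still significant.

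The test therefore rejects at 8 or more, or 2 or fewer, with or without correction. By the hypergeometric distribution, P(*a* ≥ 8) = (2025 + 100 + 1)/184,756 = 0.0115. Doubled, this is 0.0230 per test.
- Nine tests: 1 − (1 − 0.0230)⁹ = 0.189.
- By simulation (40,000 trials) at assumed common correlations of 0.3, 0.5 and 0.9: about 18%, 16% and 9–10%.

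**2. Other cut-points, two-sided.**
- 3 or fewer of 20 high: no table reaches p < 0.05, so 0%.
- 4 of 20 high: a 4-versus-0 table gives chi-square 5.0, p = 0.025. Its probability is 2 × 210/4845 = 0.0867, and 1 − (1 − 0.0867)⁹ = 0.558. With continuity correction the same table has chi-square 2.81, p = 0.094, so the rate is 0%.
- 5 of 20 high, the worst case with correction: 2 × 252/15,504 = 0.0325, and 1 − (1 − 0.0325)⁹ = 0.257.

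The range is 0 to 56% uncorrected and 0 to 26% corrected.

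**3. Median split, one-tailed 0.05 applied by halving p.**
- Uncorrected: 7-versus-3 has half-p 0.037 and rejects. P(*a* ≥ 7) = 16,526/184,756 = 0.0894, and 1 − (1 − 0.0894)⁹ = 0.570.
- Corrected: 7-versus-3 has half-p 0.090 and does not reject. P(*a* ≥ 8) = 0.0115, and 1 − (1 − 0.0115)⁹ = 0.099. A one-sided Fisher's exact test gives the same.

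**4. Continuous tests, for comparison.** 1 − 0.95⁹ = 0.370 if independent. At an assumed correlation of 0.9, simulation gives 11% one-sided and about 12% two-sided.

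**5. Power.** The assumed difference is 1.32 SD, which is what a two-sided 0.05 t-test with 10 per arm detects with 80% power (noncentral t, 18 degrees of freedom, noncentrality 1.32 × √(10/2) = 2.95). On normal data, power is 0.80 by t-test, 0.75 by rank-sum and 0.51 by median-split chi-square.

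**The case against.** The strongest reply is that the arithmetic does not establish a size. The figures run from 0 to 57%. At the median split the two-sided test is conservative, at 2.3% against a nominal 5%. The 56% comes from a split with an expected count of 2 per arm, where the chi-square approximation is poor and continuity correction brings the rate to 0. The 57% falls to 10% with the same correction. The 37% belongs to continuous tests that the plan does not specify. All of this stands. A reader might infer that the trial has a 37% or 57% false-positive rate. The documents support no single figure, because the rate is set by choices they leave open. That openness is the defect.

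Three other stronger readings also go too far:
- A reader might take seven outcomes in Trial design and nine in Statistic analysis as a contradiction. The shorter list can be a summary, and the wording in Study objectives is broad enough to include AMH.
- A reader might call chi-square wrong for every outcome. The ovulating period is not defined. If it is recorded as a category, a test for categorical data suits it. Dropping it from the median-split count changes little: 1 − (1 − 0.0230)⁸ = 0.170.
- A reader might argue that values taken while on study drug cannot show ovarian protection. That rests on pharmacology the documents do not give. They support only a request to state the timing.

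It could also be said that so small a trial is exploratory. The text does not say so: it states a primary objective, randomisation, placebo and an alpha. The fair part of this objection is that formal testing of eight secondary outcomes would be optional. One primary, with the rest labelled exploratory, is enough.

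**Conclusion.** The concern holds as a qualitative defect with a bounded illustration. Nine outcomes are compared, and a primary outcome, a multiplicity rule and an efficacy time point are all absent, so following the plan leaves open which result answers the objective. Redaction or text extraction does not explain these absences.

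The most direct reading of the stated test, a two-sided median split, gives roughly one chance in five of at least one false positive if outcomes are independent, and less if they are correlated. The cut-points, correlations, per-test level and 1.32 SD difference are assumptions, not figures from the plan. Part of the power loss reflects the small actual size of the median-split test, but that is still the power this test would have. The plan should be changed on this point before any comparison by arm.

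**What to change.** Before any comparison by arm:

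1. Name one primary outcome from the planned measurements, at one fixed time from surgery that is the same in both arms. The choice is the sponsor's; AMH is one candidate already listed.
2. Analyse it as a continuous value with one pre-specified test instead of chi-square: ANCOVA adjusted for the pre-treatment value if that is collected, otherwise a Wilcoxon rank-sum test. If the chosen outcome is truly categorical, such as ovulation returned or not, use Fisher's exact test.
3. State alpha and sidedness for that test, reconciling the one-tailed 0.05 in Sample size with an objective that asks only about a difference.
4. Report the other eight as exploratory, with confidence intervals and no significance claims.
5. State when each efficacy measurement is taken relative to study drug. Dosing is not affected.

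The cost is protocol wording and the loss of significance claims for eight outcomes. The primary time should come from measurements already planned, because the documents give no visit schedule to show whether another time would need an added visit. If a two-sided test is chosen, the difference detectable by t-test at an assumed 80% power with 10 per arm rises from 1.16 to 1.32 SD. With the rank-sum fallback, power at 1.32 SD is about 75%.

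### Hormone samples are not tied to a menstrual cycle day, and no cycle day is recorded, so the hormone comparison loses precision in patients who cycle

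*Combined protocol and SAP*

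**What the plan says.** The Study objectives section makes hormones part of the main question: "By comparing the physical and hormone indexes in the control group and experimental group, we plan to find out the effect of GnRHa". The Trial design section describes the work as "monitoring the physical ovarian change and the six hormone indexes in the two different groups". The Statistic analysis section lists what is compared: "The physical ovarian volume, six hormone indexes, AMH and the ovulating period will be monitored and compared". It names chi-square as the method. AMH appears there as an item separate from the six hormones, which are never named.

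On timing, the only statement concerns treatment: "Before and after the operation, patients in the control group will receive placebos when the experimental group will receive GnRH_a". No section gives a visit schedule, a cycle day or phase for blood draws, or a rule for patients who do not menstruate. On comparability of the arms the plan says "The situation of the two group will be almost the same considering the average age, the average BMI, the average grading evaluation". Cycle phase and menstrual status are not among those factors. The Inclusion criteria admit "Females aged 10-90 who are confirmed with ovarian malignancy and are willing to receive fertility preservation surgery", so cycling and non-cycling patients may be mixed.

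**The concern.** Some reproductive hormones are taken here to change markedly across the menstrual cycle; this is a general premise, not something the document quantifies. The plan follows ovulation as an outcome, so it expects at least some patients to cycle. If blood is drawn on whatever day a visit falls, a value from after ovulation in one patient is set against an early-cycle value in another. Part of the spread between patients then reflects the day of sampling and not ovarian function.

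With about 10 evaluable patients per arm there is little precision to lose. If the cycle day is not written down at the draw, it may not be recoverable later. Correcting other parts of the analysis would not standardise samples already taken.

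**Working it through.** **Inputs from the document.** Effective sample size 20, hence 20/2 = 10 per arm; one-sided level 0.05. The dropout step is roughly consistent: 20/(1 − 0.10) = 22.2, so 23, against the 24 planned. The Sample size section cites a previous study in which "the standard deviation was 5", but ties that figure to no outcome or unit, so it cannot show whether cycle variation was allowed for. (The 20 itself does not follow from the stated inputs: (1.645 × 5/1.0)² = 67.6. That is a separate matter; 10 per arm is used here only as the planned size.)

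**Inputs assumed.** All on the log-hormone scale: within-cycle SD w from 0.3 to 0.7, and SD between patients at a fixed phase b of 0.35 (a homogeneous cycling group) or 1.0 (a mixed group). One sample per patient, and all patients cycling.

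1. Variance ratio from unstandardised timing: R = (w² + b²)/b² = 1 + w²/b².
2. Take the effect that has 80% power at 10 per arm when R = 1: (1.645 + 0.842) × √(2/10) = 1.11 fixed-phase SDs. By the normal approximation, power at ratio R is Φ(2.4865/√R − 1.645).
3. Patients per arm needed to restore 80%: 10 × R, rounded up.

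| w | b | R | Power at 10 per arm | N per arm for 80% |
|---|---|---|---|---|
| 0.3 | 1.0 | 1.09 | 77% | 11 |
| 0.7 | 1.0 | 1.49 | 65% | 15 |
| 0.3 | 0.35 | 1.73 | 60% | 18 |
| 0.5 | 0.35 | 3.04 | 41% | 31 |
| 0.7 | 0.35 | 5.00 | 30% | 50 |

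4. The same noise seen as counts: if half of samples fall after ovulation (assumed), the two arms of 10 differ by 2 or more such patients with probability 0.503 and by 3 or more with probability 0.263 (two independent binomials, n = 10, p = 0.5). With p = 0.25 the figures are 0.435 and 0.193. This is not an extra harm; it is already contained in R.
5. Check for bias: 40,000 simulated trials with no drug effect, 10 per arm, and phase assigned at random, half in each. The one-sided t-test rejected in 4.9%, 5.1% and 5.0% at R = 1, 2 and 5. The SD of the arm difference rose from 0.45 to 0.64 and 1.00 fixed-phase SDs.
6. If timing differs by arm (assumed 50% against 25% of samples in one phase), the same test rejected in the direction of that gap in 20% at R = 2 and 27% at R = 5.

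**The case against.** A reader might infer that uncontrolled cycle timing can create an apparent drug effect. The document does not support that as a systematic error. Timing unrelated to arm adds the same noise to both arms, and a valid test keeps its level (step 5). A single small trial may show a misleading estimate, but the standard error already reflects that. A raised false-positive rate needs timing that differs by arm. Nothing in the plan prevents this, and nothing shows that it will occur.

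The size is also open to challenge. The six hormones are unnamed, so an illustration built on one strongly phase-dependent hormone would rest on values from outside the document. Not every patient will cycle: ages run from 10 to 90, and some patients have already lost the other ovary. A mixed group has a wider spread between patients, which is why the table includes b = 1.0. The plan says that hormones are monitored, which may mean repeated values. With four random-day samples averaged (assumed) and b = 0.35, R is 1.18 to 2.0 in place of 1.73 to 5.0. The calculations compare means, whereas the stated test is chi-square. All of this stands, and it makes the magnitude conditional.

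It can also be said that cycle day is one detail within a larger gap, since no assessment time is given at all, and that following ovulation supplies some cycle information. Both are true. But the plan does not link that information to the blood draws, and a general visit schedule alone would not standardise phase.

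**Conclusion.** The concern holds as a loss of precision. The hormone indexes support the objective and some patients are expected to ovulate, but sampling is neither tied to a cycle day nor accompanied by a record of one. Where patients cycle and the hormone varies with phase, an 80% power at 10 per arm falls to somewhere between about 77% (R = 1.09) and 30% (R = 5.0). That range rests wholly on assumed variances, one sample per patient and all patients cycling; fewer cycling patients or averaged repeat samples would move it towards the mild end. Bias or an inflated error rate is not established. AMH is assumed to be little affected. This is a worthwhile, inexpensive improvement that has to be made before samples are drawn.

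**What to change.** Add to the Statistic analysis section:

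- In patients who are menstruating, the cycle-dependent hormones (to be named) are drawn in one fixed early-follicular window, for example cycle days 2-4. This is done at baseline before the first study dose and at one follow-up time that is the same in both arms. Surgery is not delayed to meet the window.
- Patients without cycles, including any whose cycles stop during the study, are sampled at that same fixed follow-up time in both arms. This matters because study drug may stop cycles in one arm, and a follow-up time that depended on cycling would then let timing differ by arm.
- Cycle day and menstrual status are recorded on the case report form at every draw.
- All randomised patients stay in the main comparison, adjusted for the baseline value. This needs a method for continuous outcomes in place of chi-square for these hormones. Values inside the window are used alone only in a sensitivity analysis, reported with the number in-window by arm, because exclusion after randomisation may differ by arm and costs data at 10 per arm.
- Ovulation is judged from the separately monitored ovulating period and not from early-follicular progesterone.

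The cost is protocol wording, two form fields and some flexibility in visit dates. Some baseline samples will miss the window and are flagged. If cycles stop more often in one arm, the in-window counts will differ between arms, which is why they are reported.

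### The only stated comparison, a chi-square test, has no place for the baseline and follow-up values that monitoring change implies, and so gives up much of the information in about 20 patients

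*Combined protocol and SAP*

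**What the plan says.** The Statistic analysis section contains the whole outcome analysis in one sentence: ovarian volume, AMH, the six hormones and the ovulating period "will be monitored and compared by chi-square analysis in SPSS 17.0". The Trial design section says the effect of GnRHa will be studied "by monitoring the physical ovarian change and the six hormone indexes in the two different groups".

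Treatment lies on both sides of surgery ("Before and after the operation, patients in the control group will receive placebos", with GnRHa at the same times in the other arm). Visits are mentioned only under Safety assessments, where adverse events "will be recorded in the case report forms during each patient visit".

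The plan gives no measurement times, number of measurements, analysis time point, per-patient summary or cut-points for forming categories. It states no method for several values from one patient.

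**The concern.** Ovarian volume, AMH and hormone levels are continuous. Studying their change requires at least two values per patient. An ordinary chi-square test takes a table of counts in which each patient appears once. To use it, the analyst must cut a continuous value into categories and settle on one entry per patient, and the plan states neither step. Baseline cannot enter as a covariate, and further follow-up values cannot enter at all without a rule that the plan lacks.

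Two things are at stake. The first is precision: a trial with about 20 evaluable patients cannot easily afford to lose what the baseline and follow-up values carry. The second is that the choice of value, cut-point and handling of repeats is left until the data are in hand. One of the possible choices, entering every value as a separate observation, would make the test invalid.

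**Working it through.** **Inputs from the documents.** The Sample size section plans 12 patients per arm, 24 in all, to leave 20 after 10% loss. That step reproduces: 10 / 0.9 = 11.1, rounded up to 12 per arm. The check therefore uses 10 per arm. The plan's precision inputs do not themselves lead to 20, since (1.645 × 5 / 1.0)² = 67.6. That is a separate matter, as is the figure of 20 enrolled under Trial design.

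The previous study is one "in which the standard deviation was 5", with no outcome or unit named, so everything below is in SD units.

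**Assumptions, because the documents give no figures.** True effect 1 SD; m = 2 to 6 follow-up values per patient; equal correlation ρ = 0.3 to 0.7 between any two values of one patient, baseline included; two-sided 5% level. For the chi-square the outcome is split midway between the arm means, a favourable choice. Results come from simulation with 20,000 runs per setting, checked here by direct formula.

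**1. Chi-square at one time point.** The proportions above the cut are Φ(−0.5) = 0.31 and Φ(0.5) = 0.69. Summing the binomial probabilities of all 10-versus-10 tables with a chi-square above 3.84 gives power 0.39. Simulation: 0.38 to 0.39, with a real error of about 0.04.

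**2. t-test at the same time point.** The standardised difference is 1 / √(2/10) = 2.236 against t(18) = 2.101, giving power 0.56. Simulation: about 0.56.

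**3. Mean of follow-up values adjusted for baseline (ANCOVA).** The residual variance is V = [1 + (m − 1)ρ]/m − ρ², SE = √(0.2V), and power is about Φ(1/SE − 2.110), where 2.110 is t(17).

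| m | ρ | V | SE | Formula | Simulation |
|---|---|---|---|---|---|
| 2 | 0.3 | 0.65 − 0.09 = 0.56 | 0.335 | 0.81 | 0.78 |
| 6 | 0.7 | 0.75 − 0.49 = 0.26 | 0.228 | 0.99 | 0.98 |

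The formula runs about one to three points high. The simulated range is 0.78 to 0.98, with a real error of about 0.05.

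**4. The minimal reading: one value before, one after.** Here m = 1 and V = 1 − ρ², that is 0.91, 0.75 and 0.51 for ρ = 0.3, 0.5 and 0.7. The SEs are 0.427, 0.387 and 0.319. The formula gives power of about 0.59, 0.68 and 0.85, with the same slight optimism. The gain over chi-square remains. The gain over a plain t-test is small at ρ = 0.3 and large at 0.7.

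**5. What would happen if repeats were entered as patients.** The design effect is DE = 1 + (m − 1)ρ, and the real two-sided error is about 2[1 − Φ(1.96/√DE)]. Simulation uses the chi-square on the split outcome.

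| m | ρ | DE | Formula | Simulated chi-square |
|---|---|---|---|---|
| 2 | 0.3 | 1.3 | 0.086 | 0.066 |
| 3 | 0.5 | 2.0 | 0.166 | 0.135 |
| 4 | 0.5 | 2.5 | 0.215 | 0.182 |
| 6 | 0.7 | 4.5 | 0.356 | 0.308 |

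With m = 4 and ρ = 0.5, 20 × 4 = 80 rows carry the information of 80 / 2.5 = 32. The formula exceeds the simulation, so the simulated values are the ones to quote for this test.

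**The case against.** **Repeated measurement is inferred.** Monitoring is not a schedule, and visits are mentioned only for adverse events. This stands in part. Change implies two values per patient, but nothing shows more than one after treatment. With a single post-treatment value there is nothing to average, and the gain is that of step 4, not the 78% to 98% of step 3.

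**A reader might infer that repeats will be counted as extra patients.** The documents do not say so. The Sample size section counts its 20 as participants, which points to the patient as the unit. The 7% to 31% error is therefore a conditional warning and not a property of the stated plan.

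**A reader might also infer that repeats must be either wasted or miscounted.** That is not exhaustive. A change from baseline put into categories would keep one entry per patient and use the baseline. The plan does not specify it, and it recovers little. The SD of a change is √[2(1 − ρ)], so at ρ = 0.5 it equals 1 and a chi-square on split change again has about 39% power. The assumed effect becomes 1 / 1.18 = 0.85 SD at ρ = 0.3 and 1 / 0.77 = 1.29 SD at ρ = 0.7, so this route does worse or better accordingly, and it still pays the cost of splitting.

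**This is only the fault of using chi-square on continuous data.** Partly so: that accounts for the step from 39% to 56%. Moving to a t-test would cure it and still leave baseline and repeats unused.

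**The level differs from the plan's.** The plan states "We assumed an one-tailed α error of 0.05 and a sampling error of 1.0", whereas the check is two-sided. A one-tailed level raises all three powers and leaves their order unchanged. For pooled repeats the one-sided formula gives 7.5% to 21.9%.

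**Conclusion.** The concern holds in a limited form. The one stated comparison suits neither continuous outcomes nor values that belong to the same patient, and the plan supplies no step that would make it suit. At 10 per arm and an assumed 1-SD effect, the cost is power of about 39%, against about 56% for a t-test at one time point and 78% to 98% for a baseline-adjusted analysis of several follow-up values. If there is only one follow-up value, the last figure is roughly 59% to 85% by formula.

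These sizes rest on an assumed effect, number of values and correlation, none of which the documents give. They show the order of the loss and are not a forecast for any named outcome. The direction does not depend on the exact values within the range examined. The point should be acted on because the remedy is cheap. It does not show that the planned test has an inflated error rate: used once per patient at a pre-chosen cut-point, the chi-square had a real error of about 4%.

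**What to change.** For each continuous outcome, replace the chi-square test with a comparison of arms that takes the patient as the unit. Either of these will serve:

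- ANCOVA on the post-treatment value, or on the mean of the post-treatment values if there are several, adjusted for the pre-treatment value.
- A linear mixed model with patient as random effect, visit as factor and baseline as covariate (SPSS MIXED).

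State the measurement schedule and name the visits that enter. Define baseline as a value taken before the first study treatment: because treatment begins before surgery, a value that is merely pre-operative may already reflect it. State that several values of one patient will not be entered as separate observations. Keep chi-square, or an exact test, for outcomes that are truly categorical.

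The cost is analysis wording only, provided a pre-treatment value is already to be collected for each outcome; if not, one more measurement per patient is needed. There is a small downside. A mean over visits describes an average effect and may mix values taken during and after dosing, so by-visit values should be shown descriptively alongside it.
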